### **Phase I. Open trial and RCT**

**Study overview.** In this treatment development grant, 70 adolescents in Probation will be recruited to participate in the study. The first 10 will participate in an iterative development open trial. Then 60 youth will be randomized to: 1) the screening/brief intervention safety planning intervention, or 2) standard practice.

**Open Trial Design.** A total of 10 youth will be recruited for open trial in order to: a) test the protocol's applicability in Probation, and b) train the mental health counselors in the protocol. We have used this 2 phase approach extensively in prior studies. The open trial will occur in months 5 - 8 after counselor training. The protocol and procedures will be modified as necessary after the first 5 participants and then again after 10 pilots have been run through the protocol and prior to conducting the pilot RCT

[figure not shown]
**Overview of RCT Trial Procedures.** When youth arrive for their first Probation appointment, they are asked to complete the MAYSI/NSSI assessment. Youth who flag in on the MAYSI or NSSI item on this first screen, will be referred by their PO to the mental health counselor who will approach them about participation in the study. If the parent/caregiver consents to the study, the mental health counselor will then meet with the youth, physically separate from the parent/caregiver, to describe study procedures in detail (**including the fact that only youth who are positive on the secondary screen continue in the study**) and obtain juvenile assent without parental presence (see **Human Subjects**). Consenting procedures will also include permission to access court records. All youth will then complete the complete the Self-Injurious Thoughts and Behaviors Interview 2.0 (SITBI-Short Form^91, see below), to more thoroughly assess self-injurious behavior. Families will then be referred back to their PO to complete the secondary screen. If the youth screens in, he/she is then randomized to either standard practice or the safety planning intervention.

Follow-up assessments will also be completed at 1- and 3-months post-baseline to gather data on youth outcomes related to treatment, self-harm, and recidivism. No juvenile will ever be sanctioned by the court for not agreeing or being unable to participate in the research study (see **Human Subjects/Letter of Support**).

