unable to reach the participant using the above information. Participants will be asked to sign a letter addressed to each of their locators that explains that they are participating in a research project. Locators will be contacted only if all efforts to reach the patient have failed. Weekly case review meetings will review no-shows, non-verified and non-confirmed cases and activities necessary to ensure successful completion of the follow-up assessments. We have used these procedures with success in other projects. Participants will be contacted 1 week prior to each follow-up appointment. The phone-based follow-ups will assist with retention. In MPI [name]'s NIAAA-funded study with CINI youth, retention rates were 94% at 3 months and 84% at 6 months.

**Training in Assessment.** Training in the follow-up assessment protocol will occur during the first 3 months. Similar to the other JJS-involved protocols for MPI [name]'s other NIH-funded RCT projects, a primary bachelor's level research assistant (RA) will be trained to administer and score the assessment protocol for 1 and 3-month follow-ups. Under MPI [name]'s oversight, the RA will receive training on working in the JJS and on how to appropriately respond to logistical questions that participants' may have.

**Procedures for MH Deterioration/Safety Concerns.** It is possible that some participants will report symptoms that may warrant additional mental health care. POs routinely refer to community mental health clinics, as part of standard procedure, youth with any other emotional/behavioral problems in addition to self-injury. Our research team has conducted a number of studies involving assessment of self-injury (e.g. MH095786, MH090147, MH082211) and, as such, has developed procedures for managing self-injury when necessary at follow-up interviews (detailed in Human Subjects and **Appendix 2**).

**Phase I Measures (see Appendix 3).** The selection of measures was designed to be realistic for the JJS with an emphasis on eventual implementation in a larger effectiveness trial. The measures below will be collected electronically or by paper and pencil, if necessary, when there is limited internet access in Probation or on home visits.

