**Primary Aim.** Our primary aim is to examine feasibility and acceptability of the safety planning intervention to inform next-step study design. **Feasibility** of a larger future trial will be evaluated based on: a) enrollment rates for the research project (target = 70%), and feasibility of the intervention, b) the percentage of participants who complete the entire intervention protocol (target = 70%). We will also determine the appropriateness of our assessment battery for a larger, future trial, by examining whether the range of responses to instruments indicate sufficient variability and change over time. **Acceptability** will be demonstrated by study withdrawal (< 20%) and > 80% of the responses on a consumer satisfaction scale rated as highly satisfactory. We will use logistic regression to model binary outcomes of enrollment, completion of the protocol, and withdrawal as a function of treatment assignment. We will use ordinal logistic regression for the satisfaction scale analysis.

With respect to youth level clinical outcomes, the goal is to obtain a reasonably precise estimate of the standard deviation for the outcome variables, and pre-post correlations of outcome variables, which are essential statistics for powering a definitive trial. Following Leon et al (2011) and Kraemer et al (2006), our goal is not to obtain a preliminary estimate of the treatment effect size, but as per Teare and colleagues (2014), the size of the pilot we propose is sufficient to obtain sufficiently precise estimates of key variance and covariance parameters necessary to design a definitive trial. Our approach will be to conduct an analysis consistent with the testing of the hypothesis that JJS youth enrolled in the experimental condition have less self-injurious ideation and behavior at 1 and 3 month follow-up relative to youth enrolled in standard practice. We will also examine mechanisms including treatment attendance, safety skill acquisition, motivation for

treatment, and treatment barrier reduction. The main outcomes are suicidal ideation and suicide attempts/NSSI on the SITBI.

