**Power:** We will recruit 70 participants in the RCT which should be sufficient to make judgments regarding feasibility and acceptability. We do not have pilot data available for calculating effect sizes to present here because R34 applications do not require pilot data but are used to collect pilot data regarding feasibility and acceptability. Two-way comparisons across treatment groups result in 80% power to detect effect sizes amounting to standardized mean differences (Cohen's d) of 1.0 or higher as statistically significant under a two-sample t-test analytic framework. With repeated measures for outcomes, under assumptions of reasonable reliability for the outcomes ( $r = .8$ ) and high autocorrelation for repeated measures ( $r = .64$ ), we will be able to detect smaller differences ( $d = .62$ ) in pairwise comparisons (where  $.62 = (16*(1-.8^2)/15)^{0.5}$ , following Lehr [137]). A medium ES when power is set at .8, is typically considered a clinically relevant finding. Thus, if high levels of feasibility and acceptability are found, this would suggest that the protocol should be tested in a larger trial. For power of .8 and a clinically relevant ES, i.e., a medium ES ( $d = .5$ ), a sample of 64 per group would be required in a future R01.

**Aim 2: Service level mechanisms** will be examined as potential mediators of intervention effects. Success of treatment linkage, including barriers to outpatient treatment, and the equity of intervention fidelity and treatment linkage across sex, race, and ethnicity will be compared following the analytic approach summarized in Aim 1.

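### The pilot's size is called sufficient to judge feasibility and acceptability, but no precision is given; a minimal pass on 70% completion in about 30 recipients has a 95% interval of 51% to 85%

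*Combined protocol and SAP*

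**What the plan says.** The Primary Aim paragraph of the Phase I Data Analysis Plan makes feasibility and acceptability the main purpose of the trial. Feasibility rests on "enrollment rates for the research project (target = 70"%) and on "the percentage of participants who complete the entire intervention protocol (target = 70"%). Acceptability rests on withdrawal below 20% and more than 80% highly satisfactory ratings. No interval, minimum acceptable value or error rate accompanies any of these. The method named for the binary outcomes is logistic regression of enrollment, completion and "withdrawal as a function of treatment assignment".

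The Power paragraph gives the RCT 70 participants, "which should be sufficient to make judgments regarding feasibility and acceptability". The calculations that follow all concern Cohen's d, although the Primary Aim paragraph says that estimating the treatment effect is not the goal. The Power paragraph then says that high feasibility and acceptability would point toward a larger trial.

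On size, the Study overview in Phase I reads differently: "The first 10 will participate in an iterative development open trial", and "Then 60 youth will be randomized to: 1) the screening/brief intervention safety planning intervention, or 2) standard practice". On loss, the Protection against Attrition paragraph reports that in an earlier study by the team "retention rates were 94% at 3 months and 84% at 6 months".

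**The concern.** The statement that the size is adequate for the primary aim has nothing behind it. A percentage observed in about 30 youth is imprecise, and the plan compares it with 70% as if it were known. A result that just meets the target could be written up as having shown 70% completion, although true rates well below that remain plausible.

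The planned model does not fill the gap. It compares arms; it never compares a rate with its target. For two of its three outcomes there is also no arm contrast to estimate. Enrollment comes before randomization, and standard-practice youth do not receive the intervention that is to be completed. That leaves withdrawal, where a logistic model has no finite odds ratio if either arm has no events.

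At stake is how much weight a pass can carry when the next trial is proposed.

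**Working it through.** **Inputs**
- Randomized: 60 (Study overview) or 70 (Power). The allocation ratio is not stated. Assuming 1:1, there are 30 or 35 intervention youth.
- Completion target 70%; withdrawal criterion below 20% (Primary Aim).
- Expected withdrawal: not given. Nearby figures are a planned follow-up rate of 80% (Estimated Sample Size and Retention Rates), an anticipated loss of under 20% (Data Analysis Plan), and a 3-month loss of 100 − 94 = 6% in the earlier study.

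**1. The plan's own figures.** Lehr's formula gives √(16 × (1 − 0.8²)/15) = √0.384 = 0.62, as stated. For d = 0.5 at 80% power, the t-test needs 64 per group, as stated. Both reproduce, but neither bears on a completion or withdrawal rate. The 15 in the formula matches neither 30 nor 35 per arm.

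**2. Precision of completion (exact Clopper-Pearson 95% intervals)**

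| Completed | Observed | 95% CI |
|---|---|---|
| 21/30 (minimal pass) | 70.0% | 50.6% to 85.3% |
| 24/30 | 80.0% | 61.4% to 92.3% |
| 27/30 | 90.0% | 73.5% to 97.9% |
| 25/35 (minimal pass) | 71.4% | 53.7% to 85.4% |

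The half-width at 21/30 is (85.3 − 50.6)/2 ≈ 17 points. In 30 recipients the lower limit first exceeds 70% at 27; at 26/30 it is 69.3%.

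**3. Chance of meeting 70%.** With 30 recipients this is P(X ≥ 21), X ~ Bin(30, p); with 35 it is P(X ≥ 25), X ~ Bin(35, p).

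| True completion | 30 recipients | 35 recipients |
|---|---|---|
| 60% | 18% | 11% |
| 65% | 36% | 27% |
| 70% | 59% | 51% |
| 80% | 94% | 93% |

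**4. Other criteria have larger denominators.** Enrolling 60 at 70% or 60% acceptance means approaching about 60/0.70 = 86 or 60/0.60 = 100 youth. Minimal passes are 61/86 (60.1% to 80.2%) and 70/100 (60.0% to 78.8%). Withdrawal can use all randomized youth: the largest passing count in 60 is 11 (18.3%, CI 9.5% to 30.4%).

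**5. Withdrawal by arm.** The chance that at least one arm of n has no withdrawals is 1 − (1 − (1 − p)ⁿ)². For p = 0.06 and n = 30: 0.94³⁰ = 0.156, and 1 − (1 − 0.156)² = 0.288.

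| Withdrawal rate | 30 per arm | 35 per arm |
|---|---|---|
| 5% | 38% | 30% |
| 6% | 29% | 22% |
| 8% | 16% | 11% |
| 10% | 8% | 5% |
| 15% | 1.5% | 0.7% |
| 20% | 0.25% | 0.1% |

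Illustration, 0/30 against 4/30: the odds ratio is not finite and the Wald p is .999, but the likelihood-ratio p from the same model is .016 (chi-square 5.83) and Fisher's exact p is .11. The risk difference is 13 points, Newcombe 95% CI −1 to 30.

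**The case against.** The best defense is that this is a pilot. The plan speaks of targets that inform the next study, not of a binding rule. It also plans other evidence: variability of the assessment battery, exit interviews and stakeholder interviews. Nothing in it says that intervals will be withheld. The 70% cut-off is not useless either: with 30 recipients, a true rate of 60% misses it 82% of the time and a true rate of 80% meets it 94% of the time. Failing about two times in five at exactly 70% is what any cut-off placed at the true value does. All of this stands. It limits the point to an unsupported claim of sufficiency and to what a pass may be said to show.

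Four stronger readings are tempting, and the documents do not support them.
- **A reader might infer that any pass shows only that completion exceeds 50%.** That is true of the minimal pass; 24/30 and 27/30 show more.
- **A reader might infer that the withdrawal model will often have no estimate.** That needs withdrawal of about 5% to 6%. The 6% is loss to follow-up in a different study, which is not the same as withdrawal. At rates nearer the plan's own 20% limit the problem nearly vanishes.
- **A reader might infer that an empty arm makes the p-value close to 1.** That is a property of the Wald test, which the plan does not specify. Nor does an empty arm affect the below-20% criterion, which needs no arm comparison.
- **A reader might want fixed zones, such as met at 27 or more of 30 and not met at 15 or fewer.** These would return an intermediate result 97% of the time at a true 70% and 88% at a true 80%, so they are a debatable preference.

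**Conclusion.** The point holds as a matter of precision and reporting. The size is declared adequate for the primary aim without support, the targets are bare percentages, and the planned model tests none of them. A minimal pass on completion is compatible with true rates from about 51% (30 recipients) or 54% (35 recipients) up to 85%. With 30 recipients a true rate of 60% passes about one time in six. Both denominators assume 1:1 allocation, and the totals of 60 and 70 must be reconciled; the conclusion survives either.

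The missing odds ratio for withdrawal is a conditional risk, from 38% at 5% withdrawal to 0.25% at 20% with 30 per arm. The documents do not say where in that range the trial will fall. It is still worth avoiding, because an alternative that always gives an interval costs nothing.

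**What to change.** 1. Replace the sufficiency sentence with the precision available: about ±17 points for completion near 70% in 30 recipients. Reconcile 60 and 70 and state the allocation ratio.
2. Report each feasibility and acceptability rate with an exact 95% interval beside its target. Use intervention-arm youth for completion, all randomized youth for withdrawal, and the at-risk youth approached for enrollment. If satisfaction counts several item responses per youth, base its interval on youth, because responses from one person are not independent.
3. State that a pass whose interval includes values short of the target is consistent with that target and does not demonstrate it.
4. Report between-arm withdrawal as a risk difference with a Newcombe or Miettinen-Nurminen interval, using Firth's method if covariates are added. Remove enrollment and intervention completion from the regression on treatment assignment.
5. If the sponsor wants go, revise and stop zones, it should choose the cut-offs and state their error rates in advance.

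The cost is wording and minor analysis changes, with no added participants or data. The claim about what the pilot can establish becomes more modest.

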COVER PAGE

Date: 2-25-20

Study Protocol

: NCT03655470

Brief Title: Safety Planning in Juvenile Justice for Suicidal Youth

Official Title: Screening and Brief Intervention for Suicidality and Nonsuicidal Self-Injury Among Youth in the Juvenile Justice System

Secondary IDs: 1R34MH114307-01A1 [U.S. NIH Grant/Contract Award Number]

The proposed study will be divided into two phases. In Phase I, we will conduct an open trial with 10 adolescents which will allow us to make any modifications necessary for using the protocol in Probation. We will then randomize 60 suicidal JJ youth who screen positive for recent SI into standard care or the safety planning intervention. We will train two part-time counselors who have a master's degree in the mental health field and work in the local community mental health clinic, Gateway, in which MPI [name] and Co-I [name] have consulted. Counselors with community mental health experience were selected because youth in the JJS are typically served by community mental health clinics, so this choice was also made with an eye toward eventual implementation. In addition, the model proposed here – of mental health counselors embedded in Probation – is consistent with a co-responder model, found across the U.S. in which a PO works collaboratively with a mental health professional to coordinate care. Thus, if the protocol is found to be effective, there is an existing infrastructure that could aid further implementation. We will hire a bilingual counselors so they will be able to conduct the intervention and give feedback to youth and parents who are Spanish-speaking.

The counselors will cover afternoon appointments in Probation and be employed by the research grant because Probation rules prohibit audiotaping sessions with youth. By employing the mental health counselors on the grant, we will be able to rate tapes of sessions for fidelity and competency (see below). In order to conduct the study under conditions most relevant to a future implementation trial, we will also employ a training approach that has been successfully implemented by Co-I [name] with Bachelors and Masters level staff in a psychiatric hospital (see below)..

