representation will be about 22% Africa American or Black (and other) and 72% White. **Estimated Sample Size and Retention Rates.** In 2016, the RIFC handled offenses for 2,634 juveniles of whom 764 (29%) were female and 2,581 (98%) who were in the 12-17 year old age range. The Juvenile Intake Department, for example, screens more than 904 juveniles per year and, of those youth who are screened, approximately 10% (N=89) flag for recent SI. In 2015, the detention center admitted 470 youth. *Probation had a caseload of 375 in 2015. Of these youth, it is estimated that 20% of youth screen positive for current risk of self-injurious behavior (N=75). Even with a conservative acceptance rate of 60%, we would be able to recruit about 45 youth per year and meet our 20 month projected enrollment goal of 60 participants, i.e. about 3 per month (3 x 20 = 60). Using a conservative follow-up rate of 80% (see **Retention**) of the 60 enrolled and retained participants, approximately 48 are expected to complete the 3-month follow-up.* This approach is feasible given our excellent working relationship with the JJS, including the RIFC, and prior experience recruiting from the juvenile intake department (see RIFC Chief Judge and Probation Letters of Support). MPI [name] collaborated on a 24-month longitudinal epidemiological study of first-time CINI offenders at the RIFC and we successfully recruited the entire sample of 400 first-time offending CINI youth (DA034538). MPI [name] is also currently recruiting at the RIFC juvenile intake department for a baseline sample of suicidal CINI youth for her NIMH K23 Mentored Career Award. MPI [name] also successfully established a referral system from RIFC to his NIAAA (AA017659) and NIDA (DA0029871) trials for youth with substance use-related court involvement.

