### **Phase I: Data Analysis Plan**

Prior to conducting analyses for the project aims, a series of routine procedures will be conducted to ensure the data accuracy/adequacy. All forms will be checked for missing data and all data will be double entered and backed-up daily. Descriptive statistics will be examined for distributional properties of the variables (e.g., normality, internal consistency). The data will be transformed to achieve normality if needed.

We will conduct analyses in an intent-to-treat (as randomized) manner, and examine as primary analyses unadjusted and secondarily adjusted for selected covariates identified above. Masking integrity will be reviewed. ANCOVA (outcome regressed on baseline) methods will be used, and linear mixed effect models will be used to account for non-independence of repeatedly observed outcomes.

We will examine attrition by comparing follow-up assessment completers and non-completers on socio-demographic and baseline data to determine if they differ systematically. Consistent with an intent-to-treat model, we will include all randomized participants in the analyses. Attrition/Missing Data. It is anticipated that less than 20% of subjects will not have follow-up data. We will test for differential attrition across the experimental condition and the baseline comparison. The analyses described below can account for attrition at the follow-up points. We will employ multiple imputation as our primary approach to missing data [138] and will conduct a sensitivity analysis treating all participants lost to follow-up as treatment failures at the point of loss, i.e. assuming no change on their self-injury-related mechanisms or outcomes. If our primary conclusions are similar with and without extreme missing data assumptions, confidence in the findings will be higher.

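### The Power paragraph puts 70 in the RCT and divides by 15, but 60 are randomized; d = 1.0 at 80% power fits no sample size in the plan, and d = .62 is not tied to the planned test

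*Combined protocol and SAP*

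**What the plan says.** **Power paragraph (Phase I: Data Analysis Plan).** It opens: "We will recruit 70 participants in the RCT which should be sufficient to make judgments regarding feasibility and acceptability". Two-way comparisons are said to "result in 80% power to detect effect sizes amounting to standardized mean differences" of 1.0 or higher under a two-sample t-test. With repeated measures, a reliability of .8 and an autocorrelation of .64, the detectable difference is said to fall to .62, from "62 = (16*(1-.8^2)/15)^{0.5", citing Lehr's rule. Neither alpha nor the allocation ratio is given.

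**Sample size elsewhere.** The opening overview says: "We will then randomize 60 suicidal JJ youth who screen positive for recent SI into standard care or the safety planning intervention". The study overview under Phase I. Open trial and RCT recruits 70 in total and splits them: "The first 10 will participate in an iterative development open trial", and "Then 60 youth will be randomized to" the two conditions. Under Estimated Sample Size and Retention Rates the enrolment goal is 60, and with 80% follow-up "approximately 48 are expected to complete the 3-month follow-up".

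**Planned analysis.** The Data Analysis Plan will "examine as primary analyses unadjusted and secondarily adjusted for selected covariates identified above". It names ANCOVA and linear mixed models. For the clinical outcomes the main inference is the treatment effect pooled over the 1- and 3-month follow-ups, with time-specific results secondary. Under Primary Aim, feasibility and acceptability come first; for clinical outcomes the stated goal is to estimate variances and correlations, not an effect size.

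**The concern.** The 70 is the whole study, open trial included, not the RCT. The 15 stands where Lehr's rule has the number per group, and no section describes a group of 15. A detectable difference of 1.0 also looks far too large for 60 randomized participants.

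These are the only detectable-effect figures given for this trial, and the plan still commits to testing for significantly better outcomes under safety planning. As written, a reader cannot tell which sample size or which analysis either figure describes.

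**Working it through.** **Inputs.** 60 randomized and about 48 at 3 months (sections cited above). Correlation .64 and multiplier 16 (Power paragraph). Assumptions: 1:1 allocation, so 30 per arm as randomized and 24 with 3-month data; two-sided alpha 5%, since 2(z.975 + z.80)² = 2(1.960 + 0.842)² = 15.7, which is about the plan's 16; 80% power.

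**1. The plan's own figure.** √(16 × (1 − .64)/15) = √(5.76/15) = 0.620, so .62 follows from the formula as printed. The same value arises from a change score with 30 per arm: √(16 × 2 × (1 − .64)/30) = 0.620. The number alone therefore does not identify n.

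**2. Where d = 1.0 comes from.** Lehr's rule for a plain two-group comparison is d = 4/√n. Exact values use the noncentral t.

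| n per group | Lehr d | Exact d | Power at d = 1.0 |
|---|---|---|---|
| 15 | 1.03 | 1.06 | 75% |
| 16 | 1.00 | 1.02 | 78% |
| 17 | 0.97 | 0.99 | 81% |
| 24 | 0.82 | 0.83 | 92% |
| 30 | 0.73 | 0.74 | 97% |
| 35 (if 70 were randomized) | 0.68 | 0.68 | 98.5% |

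Only about 15 to 17 per group gives 1.0. Allocation of 2:1 does not rescue it: d = 0.78 at 40/20 and 0.88 at 32/16.

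**3. Consistency of the two figures.** At 15 per group they agree with each other: 1.03 × √.36 = .62. If .62 was instead a change-score result at 30 per arm, the preceding sentence should have read 0.73, not 1.0. One of the two figures is wrong on either reading.

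**4. The test the plan puts first.** For the unadjusted mean of two follow-ups with correlation ρ, the variance factor is f = (1 + ρ)/2, and the detectable d is √f times the exact two-sample value. At ρ = .64, f = .82 and √f = .906:

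- 30 per arm: .906 × 0.736 = 0.67; power at d = .62 is 74%.
- 24 per arm: .906 × 0.826 = 0.75; power at d = .62 is 64%.

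For ρ from .4 to .8 the detectable d is 0.62 to 0.70 (30 per arm) and 0.69 to 0.78 (24). Power at .62 is then 81% down to 70%, and 71% down to 60%. A simulation with 20,000 replicates at ρ = .64 agreed with the power at .62 to within one percentage point.

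**5. Other analyses the plan could mean.**

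| Analysis | Variance factor | d, 30 per arm | d, 24 per arm |
|---|---|---|---|
| Pooled, baseline-adjusted, baseline correlation .64 | .82 − .64² = .410 | 0.47 | 0.53 |
| Same, baseline correlation .5 | .82 − .5² = .57 | 0.56 | 0.62 |
| ANCOVA at one time point, baseline correlation .64 | 1 − .64² = .590 | 0.57 | 0.64 |
| Change score, correlation .64 | 2(1 − .64) = .72 | 0.62 | 0.70 |

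**6. Future trial.** The 64 per group for d = .5 reproduces: 16/.25 = 64, and exact t also gives 64.

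**The case against.** The strongest reply is that the 15 may be half of 30. On the change-score reading the formula uses the correct arm size, and .8² is simply the stated autocorrelation of .64 in awkward notation. That reading is possible and the origin of 15 cannot be settled from the documents. But it leaves d = 1.0 wrong, and the plan names ANCOVA and mixed models, not change scores.

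Second, whether .62 is optimistic depends on the model. The plan calls unadjusted analyses primary and then says ANCOVA on baseline will be used. With baseline adjustment, .62 is conservative for the pooled effect (0.47 to 0.53), and the single-time-point ANCOVA results (0.57 to 0.64) bracket it. This stands: 64% to 74% power applies to the unadjusted pooled test only.

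Third, alpha is not stated. With 24 per arm, d = 1.0 would have 80% power at two-sided alpha .0125. Nothing in the plan suggests that level, and the multiplier 16 points to 5%, but 5% remains an assumption.

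Fourth, the d = 1.0 error is cautious, no go/no-go rule uses either figure, and the sample size is justified by feasibility. All true. It limits the seriousness, but does not make the figures right.

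**Conclusion.** The concern holds. That 70 in the RCT contradicts 60 randomized needs no assumption. Given 1:1 allocation and two-sided 5%, d = 1.0 is not what this trial detects with 80% power: the figure is 0.74 (30 per arm) to 0.83 (24 per arm). The d = .62 reproduces arithmetically but is tied to no analysis the plan names. For the unadjusted pooled test it is somewhat optimistic; with baseline adjustment it is generally conservative.

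The 24 and 30 figures are approximate bounds. Mixed models and multiple imputation keep all randomized participants, but how much information is recovered depends on 1-month retention, which is not given. All these values concern continuous outcomes; they do not cover suicide attempts if those are analysed as binary or as a rare count.

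This should be fixed, but it does not threaten the trial: the primary aim is feasibility and acceptability, and the 64 per group for a future trial is correct as an evaluable number.

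**What to change.** In the Power paragraph:

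- Replace the 70 in the RCT with 60 randomized (30 per arm if 1:1), about 48 expected at 3 months.
- State alpha and the allocation ratio.
- Say whether the primary model for clinical outcomes includes baseline.
- Delete d = 1.0, d = .62 and the formula with 15, and insert text such as:

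> With two-sided alpha .05 and 80% power, a two-sample t-test detects d = 0.74 (30 per arm, no loss) to 0.83 (24 per arm). For the primary unadjusted group effect pooled over 1 and 3 months, assuming a correlation of .64 between follow-ups, the detectable d is about 0.67 to 0.75. For the secondary baseline-adjusted analysis, assuming the baseline-to-follow-up correlation is also .64, it is about 0.47 to 0.53.

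If baseline adjustment is meant to be primary, exchange those labels. If a change score was intended, name it in the analysis plan and give 0.62 (30 per arm) to 0.70 (24 per arm). Leave the 64 per group as it is.

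The cost is rewording one paragraph, with no change to enrolment, design or procedures.
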